2.1.2.2 Visit windows after study drug discontinuation

For summaries of data collected after study drug discontinuation, data from both treatment epoch and safety follow-up epoch will be considered. Participants who prematurely discontinue the study drug will be required to have their EOS visit as soon as possible and enter into the SFU according to the assessment schedule in protocol Table 8-2. In the SFU, all assessments are relative to EOS visit. Day 1 will be the first day after EOS visit. The visit window definitions for SFU Visit 1 and Visit 2 are provided in Table 2-11. The SFU Visit 2 will be the last clinic visit and the end of SFU Visit will be performed by telephone contact. Additional SFU Visit will be required if participants have either IgG or IgM < screening or LLN, and they will be performed outside of the study.

Table 2-11 Visit-windows after study drug discontinuation

Visit-window	Start day	Target day	End day
SFU Visit 1	1	84	126
SFU Visit 2	127	168	210

2.1.2.3 Multiple assessments within visit windows

It is possible that multiple assessments of a participant fall into the same visit-window (e.g. due to unscheduled visits). All results (scheduled and unscheduled) will be displayed in listings, but only one value (observed or derived) will be selected for summary statistics by visit-window.

For quantitative variables, the assessment closest to the target day will be selected. If more than one assessment is at the same distance to the target day, the later one will be selected. For tables displaying the worst case scenario, such as shift tables or notable abnormalities, all assessments within a visit window will be used to identify the worst (e.g. the maximum or the minimum depending on parameter). Where applicable it will be defined for each parameter what the worst case is.

For qualitative variables, the worst record is selected; it is noted that in the relevant data subsection, worst case is always well defined.

2.2 Analysis sets

The Full Analysis Set (FAS) comprises all subjects to whom study drug has been assigned and who received at least one dose of study drug. The FAS will be used for the summary of demography and baseline characteristics as well as for all efficacy analyses except CC

The Safety Set (SAF) includes all subjects who received at least one dose of study drug. The SAF will be used for all safety analyses.

Please refer to appendix Table 5-2 for subjects to be excluded from analysis.

2.2.1 Subgroup of interest

Subjects enrolled into the study are previously treated with either fumarate-based therapies or Fingolimod. The following efficacy subgroups will be analyzed as part of CSR:

- Last prior DMT (fumarate-based therapies vs. fingolimod)
- Duration of washout (<30 days vs. ≥30 days)
- Baseline NfL (<median of baseline NfL and ≥median of baseline NfL)

The primary endpoint analysis and part of exploratory endpoint analyses (MRI, NfL, 6mCDW, NEDA-3 and EDSS) will be repeated for last prior DMT subgroup. The primary endpoint will be repeated for duration of washout and baseline NfL subgroups separately. The primary endpoint and MRI endpoints (number of T1 Gd+ lesions and number of new or enlarging T2 lesions) will be analyzed by last prior DMT and duration of washout together.

The following safety subgroups will be analyzed as part of CSR:

- Last prior DMT (fumarate-based therapies vs. fingolimod)
- Duration of washout (<30 days vs. ≥30 days)
- Injection related premedication category

The analysis of injection related reaction (IRR) will be repeated for injection related premedication category subgroup. Details of premedication categories are specified in Section 2.4.2.3. TEAEs will be repeated by last prior DMT and duration of washout subgroups. Special lab results (IgG, IgM, lymphocyte and neutrophil) will be repeated by last prior DMT subgroup.

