Exploratory objective(s)	Endpoint(s) for exploratory objective(s)		
Demonstrate effectiveness of ofatumumab 20 mg s.c. administered every 4 weeks	 Change from Baseline during the treatment period, of the following Assessments: EDSS Timed 25-Foot Walk (T25FW) Nine-Hole Peg Test (9HPT) COIIIIIIIIIIIIIIIIIIIIIIIIIIIIIIIIIIII		

Objective(s)	Endpoint(s)
Explore patient reported outcomes in subjects treated with ofatumumab 20 mg s.c. administered every 4 weeks	 Change from Baseline during the treatment period of the following Assessments: The impact of MS disease as measured by the CCI CCI CCI CCI
Explore Neurofilament (NfL) light chain as a biomarker for MS in terms of prognosis and disease activity monitoring	 Change from baseline in serum NfL light chain concentration Relationship between baseline serum NfL and disease activity, disease course and treatment response Correlation of serum NfL measures and MRI activity signs /Gd+ or new / enlarging T2 lesions) for disease activity monitoring
Explore serum CCI for MS progression	 Change from baseline in serum CCI Relationship between baseline serum progression (EDSS) and treatment response Correlation of serum CCI measures and MRI activity signs /Gd+ or new / enlarging T2 lesions) for disease activity monitoring Correlation between serum CCI levels and NfL serum levels in the course of MS disease
Explore the utility of using the CCI application	Adherence to CCI assessments quantified as CCI Correlation between CCI assessments and other assessments performed in the study CCI CCI includes the following:
Explore daily activity and slee patterns via CCI	

3 Study design

This is a single arm, prospective, multicentre and open-label, 96-week study to evaluate the treatment effectiveness of ofatumumab (OMB157) in subjects with relapsing MS transitioning from any fumarate-based RMS approved therapy, such as DMF or DRF, or fingolimod due to breakthrough disease activity. A total of approximately 555 eligible subjects will receive open-label ofatumumab 20 mg s.c. every 4 weeks (after an initial loading dose regimen of three weekly 20 mg doses in the first 14 days).

The study is divided into three parts: Part 1 - Screening period, Part 2 - Treatment period, Part 3 - Safety follow-up

Part 1 - Screening (and transition) period

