- Utility of **CCI** for disease activity and progression monitoring
- Correlation between CCI and NfL serum levels in the course of MS disease

Change in NfL and CCI concentration will be summarized by visit descriptively. Relationship between NfL and CCI with disease activity, disease course and treatment response will be analyzed along with utility of NfL and CCI for disease activity and progression monitoring. FAS will be used as analysis set. More details will be provided in the SAP.

PROs:

The following endpoints will be explored for the health outcomes in subjects treated with ofatumumab 20 mg s.c. once q4 weeks:

[figure not shown]
- Change from baseline in CCI
- Change from baseline in **CC**
- Change from baseline in CCI
- Change from baseline in **CCI**

Change from baseline in CCl scores, CCl scores and CCl scores will be summarized by visit descriptively. FAS will be used as analysis set.

The **CCI** consists of two sub-scores: the **CCI** for **CCI** and **CCI** for **CCI**. Descriptive statistics for **CCI** and **CCI** score at each visit with changes versus baseline will be provided.

CCI :

Adherence to \square assessments is measured by proportion of study weeks with at least 3 days of completed active testing, and proportion of study weeks with at least 3 days of passive monitoring for ≥ 4 hours/day.

Confidential

Page 91

and other clinical assessments will be evaluated only if a sufficient compliance level is attained.

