1.2 Study objectives and endpoints

Table 1-1 Objectives and Endpoints

Objective(s)	Endpoint(s)		
Primary objective(s)	Endpoint(s) for primary objective(s)		
Demonstrate the effectiveness of ofatumumab 20 mg s.c. administered every 4 weeks in subjects with relapsing forms of MS who had breakthrough disease on fumarates or fingolimod	Annual relapse rate (ARR, based on confirmed relapses) measured over the 96 weeks		
Secondary objective(s)	Endpoint(s) for secondary objective(s)		
Evaluate the safety of ofatumumab 20 mg s.c. administrated every 4 weeks in subjects with relapsing forms of MS who had breakthrough disease on fumarates or fingolimod	 Proportion of subjects with adverse events, including injection related reactions Proportion of subjects with laboratory or vital signs results meeting abnormal criteria The proportion of subjects discontinuing treatment due to insufficient effectiveness (lack of efficacy) or tolerability/safety reasons 		
Exploratory objective(s)	Endpoint(s) for exploratory objective(s)		
Demonstrate effectiveness of ofatumumab 20 mg s.c. administered every 4 weeks	 Change from Baseline during the treatment period, of the following Assessments: EDSS Timed 25-Foot Walk (T25FW) Nine-Hole Peg Test (9HPT) Low Contrast Visual Acuity (LCVA) T2 lesion volume Time to 6-month Confirmed Disability Worsening (6mCDW) based on EDSS Time to a 6-month confirmed cognitive decline (6mCCD), defined as a 4-point worsening on Number of T1 Gd+ lesions per scan Number of new or enlarging T2 lesions on MRI per year (annualized T2 lesion rate) Proportion of patients without MRI activity Proportion of subjects with No Evidence of Disease Activity (NEDA-3) as per protocol defined events during a 96-week period 		
Explore patient reported outcomes in subjects treated with ofatumumab 20 mg s.c. administered every 4 weeks	Change from Baseline during the treatment period of the following Assessments: The impact of MS disease as measured by the CCI CCI CCI CCI CCI CCI CCI CCI		
Explore Neurofilament (NfL) light chain as a biomarker for MS in terms of prognosis and disease activity monitoring	Change from baseline in serum NfL light chain concentration		

Objective(s)	Endpoint(s)			
• Explore the utility of using the application	Adherence to Classessments quantified as compliance level (%), which will be measured in terms of Classessments and other assessments performed in the study CCI includes the following: CCI CCI CCI CCI CCI CCI CCI C			

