2.5.2 Statistical hypothesis, model, and method of analysis

The primary analysis will describe the test for null hypothesis (H0):ARR >=0.18 versus alternative hypothesis (H1): ARR<0.18.

[figure not shown]
In the analysis, the response variable is the number of confirmed relapses observed from each participant and the participant's time in study (natural log of time in years) is used as an offset variable to adjust for the varying lengths of participant's time in the study. The adjusted ARR (i.e., model-based estimate adjusted for covariates) along with the corresponding one-sided 95% confidence interval and one-sided p-value for hypothesis testing will be obtained.

A negative binomial model with log-link and subject's time in study (as natural log of time in years) will be used as an offset with number of relapses in previous year, baseline EDSS, baseline number of T1 Gd-enhancing lesions, the participant's age at baseline and prior MS therapies (fumarates or fingolimod) as covariates.

In addition, ARR time-based and subject-based will also be summarized based on only confirmed relapses. Below are the definitions time-based and subject-based ARR:

- ARR (time-based) is calculated by taking the total number of relapses observed for all subjects, divided by the total number of days in study of all subjects and multiplied by 365.25 days.
- ARR (subject-based) is the individual subject ARR which is calculated by taking the total number of relapses observed for a subject divided by the total number of days in study of that subject and multiplied by 365.25.

2.5.3	CCI		
2.5.4	CCI		
missing a	t random, and constant relapse rate over time.	drop-out,	information is
2.5.5	CCI		

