2.14.10 Biomarkers (NfL)

Serum Neurofilament (NfL) concentration will be explored related to biomarker for MS. Change in NfL concentration will be summarized by visit descriptively using FAS. The arithmetic mean, arithmetic standard deviation, the mean, median, min, max, Geometric-mean, the coefficient of variation of arithmetic mean (%) and the coefficient of variation of the Geometric-mean (%), will be reported in descriptive summaries. In addition, NfL will also be summarized by visit and last prior DMT (fumarates vs. fingolimod). The mixed model for repeated measures (MMRM) on log-transformed change from baseline NfL will also be fitted, with last prior DMT and time points as factors, baseline age and the log-transformed NfL baseline concentration as continuous covariates. Unstructured correlation matrix will be specified within the model. Estimates for each time point, as well as 95% CI and p-values will be given. This analysis will also be repeated by last prior DMT. In case model has convergence issues, the following actions will be taken: 1) Drop age; 2) Change the covariance structure from unstructured to Autoregreesive(1). Details of MMRM model and SAS codes will be given in Section 5.4.4.

Serum CCI will be analyzed separately outside of CSR.

[figure not shown]

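### In the visible SAP, baseline NfL is linked to relapses only through a median split with no NfL rate ratio; one exploratory model with continuous log NfL would estimate the relationship that the protocol asks for

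*SAP*

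**What the plan says.** Protocol Table 2-1 gives the exploratory objective "Explore Neurofilament (NfL) light chain as a biomarker for MS in terms of prognosis and disease activity monitoring". One of its endpoints is "Relationship between baseline serum NfL and disease activity, disease course and treatment response". Protocol 12.6 repeats the commitment, saying that the relationship with "disease activity, disease course and treatment response will be analyzed along with utility of NfL", and refers to the SAP for more detail.

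For this objective, SAP Table 1-1 lists only "Change from baseline in serum NfL light chain concentration". Baseline NfL meets the relapse endpoint in one visible place, SAP 2.2.1. There it is an efficacy subgroup, "Baseline NfL (<median of baseline NfL and ≥median of baseline NfL", and "The primary endpoint will be repeated for duration of washout and baseline NfL subgroups separately".

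The primary model in SAP 2.5.2 adjusts for relapses in the previous year, EDSS, T1 Gd-enhancing lesion count, age and "prior MS therapies (fumarates or fingolimod) as covariates". NfL is not in that list. SAP 2.14.10 does use "the log-transformed NfL baseline concentration as continuous covariates" (together with age), but in a repeated-measures model whose outcome is change in NfL, not relapse.

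The titles and most of the content of SAP 2.5.3 to 2.5.6, the list in SAP 4 and the text of SAP 5.4.2 are redacted or missing from the public copy.

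**The concern.** A prognostic question asks how the relapse rate changes as baseline NfL rises. Repeating the primary analysis in each half gives two ARRs, each set against 0.18. As far as the visible text goes, it gives no estimate of the difference between the halves and no interval for it. The reader would compare two numbers by eye, each resting on about 82 relapses at the assumed ARR.

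The split also treats a value just above the median like the highest value in the study. Because the cut is the sample median, it moves with the population enrolled, so the result is hard to carry to another study. What is at stake is the precision and usefulness of one exploratory biomarker result.

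**Working it through.** The documents state no NfL effect size, distribution, dispersion, alpha or power, so there is no planned figure to reproduce. The sample-size derivation for the primary test is redacted.

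**Inputs from the documents.** N is about 555 (SAP 1.1). Follow-up is 96 weeks = 672 days = 672/365.25 = 1.84 years. The assumed ARR is 0.16 (SAP 3). Expected relapses = 555 × 1.84 × 0.16 = 163, or about 82 per half.

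**Assumed inputs.** Log NfL is normal with a log-linear effect on the relapse rate. The rate ratio (RR) per SD is 1.1 to 1.6 and the negative binomial dispersion k is 0 to 2. The test is a two-sided 5% Wald test with no other covariates.

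**Information kept by the split.** For a standard normal X, the covariance with the indicator X ≥ median is 1/√(2π) = 0.399, and the indicator's SD is 0.5. The correlation is 0.399/0.5 = 0.798, and its square is 0.637 = 2/π. This is like analysing 0.637 × 555 ≈ 353 subjects with the continuous variable.

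**Power.** For continuous log NfL, the noncentrality is ln(RR) × √(555 / (1/(0.16 × 1.84) + k)). For the split, multiply by √(2/π) = 0.798. Example with RR 1.25 and k = 1: 0.2231 × √(555/4.397) = 0.2231 × 11.23 = 2.51, giving 70.8% power. For the split, 2.51 × 0.798 = 2.00, giving 51.6%.

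Formula results at k = 1:

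| RR per SD | Continuous | Median split | Loss (points) |
|---|---|---|---|
| 1.1 | 18.7% | 13.4% | 5.3 |
| 1.2 | 53.5% | 37.2% | 16.3 |
| 1.25 | 70.8% | 51.6% | 19.2 |
| 1.3 | 83.8% | 65.2% | 18.6 |
| 1.4 | 96.6% | 85.5% | 11.1 |
| 1.6 | about 100% | 98.8% | 1.2 |

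For RR 1.2 to 1.3 and k from 0 to 2, the formula loss runs from 14.2 to 19.4 points. The formula maximum over all effect sizes is 19.4 points, or 16.9 with a one-sided 5% test.

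**Simulation check.** Negative binomial fits with estimated dispersion and an assumed 10% early dropout gave, at k = 1:
- RR 1.25: 69.1% against 49.1% (4,000 replicates)
- RR 1.3: 82.0% against 60.8% (4,000 replicates)
- RR 1.1: 17.3% against 12.4% (1,500 replicates)
- RR 1.6: 99.9% against 97.7% (1,500 replicates)

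The losses are 20.0, about 21, 4.9 and 2.2 points. With skewed or heavy-tailed log NfL and RR 1.25 to 1.3, simulated losses were about 19 to 28 points (800 replicates each, so noisier).

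**The case against.** The strongest objection is that there is no planned power to lose. SAP 2.2.1 presents the split as a subgroup display of the primary endpoint. It states no test between halves, no interaction and no alpha, and the protocol summary says that exploratory endpoints are descriptive. This stands. A reader might infer that the plan gives up a fixed amount of power for its prognostic objective, but the documents do not support that. The loss depends wholly on assumed inputs, and power serves here only as a yardstick for precision.

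A reader might also infer that the study would detect a moderate effect with continuous NfL and miss it with the split. That does not hold either. In simulations with known dispersion of 0.5 or 1 and RR per SD of 1.2 to 1.3, continuous power at an ARR of 0.10 was only 37% to 71%. At an ARR of 0.16, the split exceeded 50% in three of six settings (58%, 69%, 63%).

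A third inference would be that the SAP contains no NfL model for relapse. The redactions prevent that conclusion. The document history places subgroup work in SAP 2.5 and records the NfL subgroup in SAP 4, and the relevant text of both is hidden.

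Finally, two balanced strata are a legitimate display, and citing no guideline for the cut is no fault in an exploratory subgroup. This also stands. It does not supply the estimate of the relationship that the protocol asks for.

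**Conclusion.** The point holds as a low-cost improvement to an exploratory analysis. In the visible SAP, the relationship endpoint deferred from Protocol 12.6 has no model for relapse beyond the median split, and the split states no NfL rate ratio or contrast.

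If log NfL is normal and its effect log-linear, the split keeps about 64% of the information. In an illustrative two-sided 5% test at ARR 0.16, that means up to about 19 to 21 points of power for moderate effects. At dispersion 1 it means about 5 points for a weak effect and about 2 for a strong one. These figures include no covariates, so they are not the power of the model proposed below. The primary test of ARR against 0.18 is not touched.

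**What to change.** First confirm whether a redacted section already contains such a model. If not, add one exploratory negative binomial model on the FAS to SAP 2.2.1 and 2.14.10: the primary model (same offset and covariates) plus log-transformed baseline NfL as a continuous covariate.

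- Report the relapse rate ratio per doubling of NfL with its 95% CI, and the number of subjects without a baseline NfL value.
- Check log-linearity with a quadratic term.
- State that the rate ratio is adjusted for Gd-enhancing lesions, EDSS, age, prior relapses and prior therapy, so it describes what NfL adds to them.
- Keep the two median-split ARRs as a descriptive display.

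The cost is one extra model on data already collected, plus a log-linear assumption that can be checked. SAP Amendment 4 is dated before database lock. If the lock has since passed, label the model post hoc.

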2.3 Subject disposition, demographics and other baseline characteristics

2.3.1 Subject disposition

The number and percentage of subjects who completed the study or study drug and prematurely discontinued study or study drug will be presented, along with the primary reason for discontinuation. Data collected on the study and treatment disposition CRF pages will be used to summarize this information. The summary will be on the FAS.

The number and percentage of subjects who completed the study (i.e., treatment epoch) or prematurely discontinued study prior to the end of the treatment epoch, as well as who entered the safety follow-up will be presented, along with the primary reason for discontinuation. Data collected on the disposition CRF page will be used to summarize this information. The summary will be on the FAS.

The number and percentage of subjects in each analysis set will be presented.

Protocol deviations will be summarized by deviation categories for the FAS. Protocol deviations leading to exclusion from analysis sets will be summarized.

In addition to the pre-defined standard PD terms, Novartis has also defined 6 new protocol deviations and the corresponding relationship (health status related vs. site lockdown, participant concerns, etc.) to the COVID-19 pandemic in line with "FDA Guidance on Conduct

of Clinical Trials of Medical Products during COVID-19 Public Health Emergency" (March 2020) and "Guidance on the management of clinical trials during the COVID-19 (coronavirus) pandemic" (April 2020) from EMA as listed below. The following deviations related to the COVID-19 pandemic will be summarized.

- Missing visits
- Changes in procedures and assessments
- Planned visits not done at sites
- Changes in drug supply method
- Treatment not given
- Participant discontinuation due to COVID-19 situation

A cross-tabulation of COVID-19 related PD vs. corresponding relationship will also be produced.

In addition, COVID-19 related outcomes (e.g., COVID-19 AEs, discontinuation due to COVID-19, death due to COVID-19) will be descriptively summarized by country.

2.3.2 Background and demographic characteristics

Background characteristics include demographic characteristics (sex, race and ethnicity collected on the Demography CRF), age, height, body weight, BMI, employment status, alcohol and smoking history at baseline.

Age will be calculated from date of first administration of study drug and date of birth. Derived baseline height, body weight and BMI will be presented. These variables will be summarized for the FAS using frequency distributions (for categorical variables) and descriptive statistics of mean, standard deviation, minimum, median and maximum (for continuous variables).

Age categories: 18 to 30 years, 31 to 40 years, 41 to 55 years, >55 years

Subjects may be rescreened if they do not initially meet eligibility criteria. All assessments must be repeated, except for MRI (the original MRI may be used during rescreening if the rescreening occurs within 3 months of the original MR date). Demographic characteristics will also be summarized by last prior DMT.

